### **3.6.2 Off-Study Criteria**

- Screen failure or failure to maintain eligibility prior to initiation of treatment
- Completion of 10-year follow-up period
- Study is stopped for any reason
- Participant request to be withdrawn from study
- Non-compliance with study treatment and/or testing
- Lost to follow-up.
- Death

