## 3 STUDY IMPLEMENTATION

### 3.1 STUDY DESIGN

This is an open-label Phase II, single arm, pilot study to investigate the anti-tumor activity of SG in recurrent gynecologic cancers.

Participants will receive SG at 10mg/kg by intravenous (IV) infusion on Days 1 and 8 of every 21-day cycle in the outpatient setting. The standard dose adjustment algorithm defined in the SG package insert will be used to make decisions on dose reductions, interruptions or discontinuation of SG treatment based on adverse events that may occur during participants' treatments.

Restaging will be time-based and performed every 9 weeks ( $\pm$  1 week, approximately every 3 cycles) for the first year, and every 12 weeks ( $\pm$  1 week, approximately every 4 cycles) thereafter until disease progression or up to 5 years.

SG will be administered for a maximum of 5 years, or until participants experience adverse events requiring treatment discontinuation (see Section 3.2.1), trial withdrawal, progression, or as determined by the Principal Investigator (PI) after an integrated assessment of radiographic and biochemical data, biopsy results (if available), and clinical status (e.g., symptomatic deterioration such as pain secondary to disease). All study participants will be followed-up for 10 years after completion of therapy (see Section 3.3.1).

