  - Treatment will be outpatient and will be given until unacceptable toxicity, trial withdrawal, progression/loss of clinical benefit as determined by the treating investigator (refer to Section 3.6.1), or up to a maximum of 5 years.
- **Unscheduled Visits:** In the event of an unscheduled/unplanned visit (e.g., additional clinical assessment(s) due to toxicity), the treating investigator should use best clinical judgement as to the necessary assessments. In the event that the decision is made to continue treatment, all tests/assessments as required by the next visit on the Study Calendar (Section 3.4) should still be conducted (or repeated) within the applicable windows. If a decision is made to discontinue treatment, the participant should move to the End of Treatment (EoT) visit, with tests/assessments completed (or repeated) within the applicable windows.
- **End of Treatment Assessments:** The EoT visit will be performed up to 14 days after the participant comes off treatment (see Section 3.6.1) or before the initiation of a new anti-cancer treatment, whichever comes first.
- **30-day Safety Visit:** The mandatory Safety Follow-up (FU) visit should be conducted approximately 30 (+ 14) days after the last dose of study drug or before initiation of a new anti-cancer treatment, whichever comes first (see assessments, Section 3.4). In addition, the study team will confirm contact information for participant and a designated family member and remind participant of follow-up contact that will be conducted for survival status. If the participant cannot return to the study center for this visit, the participant may complete assessments locally, including seeing a local physician for a physical exam and local clinical laboratories, and the study team will follow-up with the participant remotely.
- **Long-term Follow-up:** Overall survival will be collected for 10 years for all study participants. Participants will be contacted remotely (e.g., phone or email) approximately every 6 months ( $\pm$  30 days) after the safety visit.

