## **3.6 CRITERIA FOR REMOVAL FROM PROTOCOL THERAPY AND OFF STUDY CRITERIA**

Prior to removal from study, effort must be made to have all subjects complete a safety visit approximately 30 days after the last dose of study medication.

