### **3.6.1 Criteria for removal from protocol therapy**

- Completion of study therapy
- Progressive disease (see Section 6.3)
- Participant request/voluntary withdrawal from the study therapy
- Adverse events that require treatment discontinuation as explained in Section [3.2.1](#)
- Intercurrent illness that prevents further administration of treatment
- The treating investigator determines further treatment on this study is not in participant's best interest
- Pregnancy
- Requirement for use of prohibited therapies as listed in Section [4.1](#)

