### 6.3.6 Overall survival (OS)

OS is defined as the length of time from start of treatment until death from any cause.

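### Non-compliance is listed as an off-study criterion, which conflicts with the promise of 10-year survival follow-up for all and could bias overall survival if non-compliance is related to prognosis

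*Combined protocol and SAP*

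**What the plan says.** The protocol keeps two lists. Section 3.6.1 gives reasons for stopping protocol therapy, for example "Participant request/voluntary withdrawal from the study therapy". Section 3.6.2 gives reasons for leaving the study. "Non-compliance with study treatment and/or testing" appears only in 3.6.2, beside death, loss to follow-up, a request to leave the study, and "Completion of 10-year follow-up period". No number of missed doses or tests is given as a threshold.

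The opening of Section 3.6 states what is wanted before someone leaves: "Prior to removal from study, effort must be made to have all subjects complete a safety visit approximately 30 days after the last dose". Survival contact is not mentioned there.

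Section 3.1 states: "All study participants will be followed-up for 10 years after completion of therapy". Section 3.3.1 states: "Overall survival will be collected for 10 years for all study participants", and describes the method: "Participants will be contacted remotely (e.g., phone or email) approximately every 6 months".

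Section 6.3.6 defines the endpoint: "OS is defined as the length of time from start of treatment until death from any cause". Section 10.5.3.2 analyses OS and PFS by Kaplan-Meier in each cohort, with medians and a ten-year OS rate. It has no censoring rule for participants who leave the study alive.

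**The concern.** A participant who misses doses or scans may still answer a phone call and may have no objection to being followed. Section 3.6.2 allows her to be taken off study, while 3.1 and 3.3.1 say she is followed for survival for 10 years. Study staff cannot carry out both.

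The statistical stake is informative censoring. Kaplan-Meier assumes that those censored have the same future risk as those who remain. If participants removed for non-compliance die sooner than the others, their deaths go uncounted and the curve sits too high. This affects OS directly. It affects PFS where death would have been the event, and possibly PFS and duration of response if scans stop as well. In a full cohort one participant is 1/22 = 4.5% of the sample. In a cohort stopped after the first stage she is 1/10.

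**Working it through.** **1. Does off study mean that survival follow-up ends?** No sentence says so. The reading rests on three features of the text:
- Stopping therapy has its own list (3.6.1), so leaving the study must mean something more.
- The off-study list contains death and the end of the 10-year follow-up, after which nothing remains to collect.
- The only data step requested before removal is the 30-day safety visit.

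**2. Is the case covered elsewhere?** Loss to follow-up (3.6.3) requires that the participant cannot be contacted. A request to leave the study has its own bullet. The non-compliance bullet therefore adds participants who are reachable and have not asked to leave. Survival contact is by phone or email about every six months, so it does not depend on dosing, scans or clinic visits.

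**3. The plan's own design figure.** The plan states no figure for OS precision or off-study losses. Its only design figure is the two-stage response rule in Section 10.3: stop if 0 or 1 of 10 respond; success if 6 or more of 22 respond; null rate 15%, target 35%. Exact binomial calculation reproduces it: type I error 0.0907 (limit 0.10), power 0.804 (target 0.80), early-stop probability 0.544 under the null. A full search confirms that this is the minimax design. Nothing in it depends on survival follow-up.

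**4. Illustration of the OS bias.**

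Input from the documents: cohort size 22 (Section 10.3). Assumptions: exponential survival; median 12 months for the other participants (Section 1.2.1 gives about 12 months for relapsed ovarian cancer on standard single agents); k participants with hazard ratio r = 2.5; removal uniformly between months 1 and 3.

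*True median.* With w = k/22 and x = 2^(−t/12), solve (1 − w)x + w·x^2.5 = 0.5.
- k = 2, t = 11.0: x = 0.5297 and x^2.5 = 0.2042; 0.4816 + 0.0186 = 0.500.
- k = 3, t = 10.53: x = 0.5443 and x^2.5 = 0.2186; 0.4701 + 0.0298 = 0.500.

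The true medians are 11.0 and 10.5 months. Against the 12.0-month median of the others, the gaps are 1.0 and 1.5 months.

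*What Kaplan-Meier would report.* Deaths before removal still count, so the large-sample estimate is slightly below 12. Let λ = ln 2/12 = 0.05776, and let G(t) be the share of the k participants not yet removed: 1 up to month 1, (3 − t)/2 from month 1 to month 3, and 0 afterwards. The observed hazard is

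h(t) = λ·[(1 − w)e^(−λt) + r·w·e^(−rλt)·G(t)] / [(1 − w)e^(−λt) + w·e^(−rλt)·G(t)].

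After month 3 it equals λ, so the median is 3 + (ln 2 − H(3))/λ, where H(3) is the integral of h from 0 to 3.

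| k | H(3) | Kaplan-Meier median | True median | Overstatement |
|---|---|---|---|---|
| 2 | 0.1879 | 11.75 | 11.00 | 0.7 |
| 3 | 0.1955 | 11.62 | 10.53 | 1.1 |

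With r = 1, H(3) = 3λ = 0.1733 and both medians are 12.0, so the bias is zero.

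*A second set of assumptions.* Here 5 to 20% of participants are removed at 1 to 6 months, with the hazard raised only after removal. Kaplan-Meier then reports about 12.0 throughout.

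| Hazard ratio after removal | True median at 5 / 10 / 20% removed (months) |
|---|---|
| 1 | 12.0 / 12.0 / 12.0 |
| 2 | 11.7 / 11.3 / 10.8 |
| 3 | 11.5 / 11.0 / 10.1 |

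The overstatement ranges from 0 to about 1.9 months (12.0 − 10.1).

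**The case against.** Four arguments limit the point.

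**The conflict is inferred.** Section 3.6.2 does not say that survival contact ends or that OS is censored on removal, and 3.1 and 3.3.1 can be read as overriding it. Section 3.6.3 also asks staff to reschedule, counsel and trace a participant after a missed visit, so removal is not automatic. A reader might infer that the protocol plainly orders survival contact to stop. It does not. What stands is that the natural reading of the list conflicts with two explicit promises.

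**Nothing ties non-compliance to decline.** A reader might assume that participants miss doses or scans because they are getting sicker. The documents give no rate of non-compliance and no such link. Section 3.6.1 already gives those who deteriorate ways off therapy that keep them on study: progression, adverse events, intercurrent illness, the investigator's judgement and voluntary withdrawal from therapy. This objection stands, so the bias must be stated as conditional.

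**Small simulated cohorts exaggerate the shift.** Simulating 6,000 cohorts of 22 under the first set of assumptions, and taking the median as the first time the curve reaches 0.5 or less, gives 10.3 rising to 11.9 months with two removals and 9.9 rising to 11.7 with three. Equal hazards still produce a rise, from 11.3 to 12.5 and from 11.3 to 12.0. With 22 complete observations this convention picks the 11th death and reads low; early censoring removes much of that. A shift of 1.6 to 1.8 months from such a simulation is therefore not all bias. Sampling error is also far larger than the effect: taking the midpoint when the curve equals 0.5, the 95% range of the fully followed median with two such participants is roughly 6 to 19 months.

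**The reach is limited.** OS and PFS are secondary and descriptive. The decision to continue or stop rests on response rate. This stands.

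**Conclusion.** The point holds as a conflict between sections with a conditional statistical consequence. Under 3.6.2 a reachable, consenting participant can lose survival follow-up that 3.1 and 3.3.1 promise to everyone, and the analysis section does not say how she would be censored.

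If non-compliance is unrelated to prognosis, Kaplan-Meier is unbiased and the cost is lost information. If those removed have a higher hazard, survival is overstated. At hazard ratio 2.5, with two or three of 22 removed at 1 to 3 months, the overstatement of a 12-month median is about 1.0 to 1.5 months measured against the other participants, or 0.7 to 1.1 months as the strict large-sample bias. The rate, timing and hazard ratio are all assumptions. The response-rate decision rule is unaffected. The change is worth making because survival status that is not collected may be hard to recover later.

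**What to change.** Reconcile Section 3.6.2 with Sections 3.1 and 3.3.1. State in 3.6.2 that a participant removed for non-compliance stays in the six-monthly remote survival follow-up unless she withdraws consent for it. State in Section 10.5.3.2 that participants not known to have died are censored for OS only at the last date known alive. Reporting off-study removals by reason and cohort would let readers judge whether any bias is likely.

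The criteria for stopping treatment need no change, and none is proposed. This wording does not restore missed scans, so progression could still go unobserved for PFS and duration of response.

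The cost is a sentence in each section and a few more phone or email contacts through a process that already exists. Sample size and the response rule stay as they are.

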### 3.6.3 Lost to Follow-up

A participant will be considered lost to follow-up if he or she fails to return for 3 scheduled clinic visits and is unable to be contacted by the study site staff.

The following actions must be taken if a participant fails to return to the clinic for a required study visit:

- The site will attempt to contact the participant and reschedule the missed visit for 2 months and counsel the participant on the importance of maintaining the assigned visit schedule and ascertain if the participant wishes to and/or should continue in the study.
- Before a participant is deemed lost to follow-up, the investigator or designee will make every effort to regain contact with the participant (where possible, 3 telephone calls and, if necessary, an IRB-approved certified letter to the participant's last known mailing address or local equivalent methods). These contact attempts should be documented in the participant's medical record or study file.
- Should the participant continue to be unreachable, he or she will be considered to have withdrawn from the study with a primary reason of lost to follow-up.

## 4 CONCOMITANT MEDICATIONS/MEASURES

Concomitant therapy consists of any medication (e.g., prescription drugs, over the counter drugs, vaccines, herbal or homeopathic remedies, nutritional supplements) used by a participant in addition to protocol-mandated treatment from 7 days prior to initiation of study treatment to the treatment discontinuation visit. All such medications should be reported to the treating investigator and recorded in the participant's medical records.

### 4.1 PROHIBITED MEDICATION

- Drugs that inhibit UGT1A1 should not be administered while on study treatment. UGT1A1 inhibitors include indinavir, atazanavir, nilotinib, and sorafenib (as well as certain herbal extracts). UGT1A1 inducers should also be avoided. Additional guidance can be found in the following link: <https://www.fda.gov/drugs/drug-interactions-labeling/drug-development-and-drug-interactions-table-substrates-inhibitors-and-inducers#table3-2>.
- Concomitant therapy intended for the treatment of cancer (including, but not limited to, chemotherapy, immunotherapy, radiotherapy, and herbal therapy), whether health authority-approved or experimental, is prohibited for various time periods prior to starting study treatment, depending on the agent (see Section 2.1.1), and during study treatment, until disease progression is documented and the participant has discontinued study treatment with the exception of palliative radiotherapy and local therapy.
- Any live attenuated vaccine therapies (e.g., FluMist®) for the prevention of infectious disease in the 4 weeks prior to initiation of study treatment, during and for 5 months following study treatment. Administration of inactivated vaccines (e.g., inactivated influenza vaccines), mRNA-based vaccines (e.g., Pfizer/BioNTech or Moderna vaccines against SARS-CoV-2) and monoclonal antibody treatment for acute treatment of SARS-CoV-2 is allowed per local regulatory guidelines.

- If the administration of a non-permitted concomitant drug becomes necessary during the trial, the subject will be withdrawn from trial treatment.

## 4.2 PERMITTED MEDICINES/INTERVENTIONS

Any medications (other than those excluded by the clinical trial protocol) that are considered necessary to protect subject welfare and will not interfere with trial medication may be given at the treating investigator/designee's discretion.

In case of surgery, SG should be interrupted for one week prior to surgery, if possible, and 2 weeks after the surgical procedure; restarting may be delayed for 4 weeks for major surgery (e.g., abdominal surgery, cranial surgery). Participants should be clinically stable prior to restarting treatment.

Participants are permitted to use the following therapies during the study:

- Prophylactic or therapeutic anticoagulation therapy (such as warfarin at a stable dose or low-molecular-weight heparin)
- Vaccinations (such as influenza, SARS-CoV-2)
  - Live, attenuated vaccines are not permitted (see Section 4.2).
- Megestrol acetate administered as an appetite stimulant
- Mineralocorticoids (e.g., fludrocortisone)
- Corticosteroids administered for COPD or asthma
- Low-dose corticosteroids administered for orthostatic hypotension or adrenocortical insufficiency

### 4.2.1 Prevention of Infusion-Related Reactions

- Corticosteroids are permitted prior to the administration of SG for the prevention of infusion-related reactions or as part of an antiemetic regimen.
- Premedication with antipyretics and H1 and H2 blockers prior to the start of the SG infusion.

In general, the treating investigator should manage a participant's care (including preexisting conditions) with supportive therapies other than those defined as cautionary or prohibited therapies (see Section 4.2) as clinically indicated, per local standard practice. Participants who experience infusion-associated symptoms may be treated symptomatically with acetaminophen, ibuprofen, diphenhydramine, and/or H2-receptor antagonists (e.g., famotidine, cimetidine), or equivalent medications per local standard practice. Serious infusion-associated events manifested by dyspnea, hypotension, wheezing, bronchospasm, tachycardia, reduced oxygen saturation, or respiratory distress should be managed with supportive therapies as clinically indicated.

### 4.2.2 Growth Factor Support

Febrile neutropenia may occur with SG. Growth factors (i.e., G-CSF) will be recommended for the therapeutic management of neutropenia and as clinically indicated. For participants with homozygous *UGT1A1*\*28 alleles (or other allows associated with reduced *UGT1A1* expression

and/or enzymatic activity) or with high risks as per ASCO guidelines, G-CSF support may be used as primary prophylaxis.

#### **4.2.3 Transfusion Support**

In prior clinical trials with SG, anemia occurred in 71% of participants (18% with Grade 3-4 anemia), and thrombocytopenia occurred in 25% of participants (2% with Grade 3-4 thrombocytopenia). Packed red blood cell (PRBC) transfusion will be allowed for the therapeutic management of symptomatic anemia and/or hemoglobin level below 9g/dL, as well as management of acute bleeding episodes. Diagnostic workup of anemia is detailed in Section [3.2.1.1.2](#). In case of iron deficiency anemia, repletion with oral iron repletion is permitted. Intravenous iron repletion is also permitted if there is a contraindication to oral repletion or actual or anticipated intolerance to iron repletion. Platelet transfusion will be allowed for bleeding prophylaxis.

#### **4.2.4 Antiemetic Support**

SG is considered to be moderately emetogenic; in TROPHY-U-01 (IMMU-132-06), 64% of participants receiving SG monotherapy experienced nausea (all grades) and 35% of participants experienced vomiting (all grades). Premedicate with a two or three drug combination antiemetic regimen according to institutional practice standards and/or national guidelines. Intravenous fluids (IV fluids)/electrolyte repletion may be administered to support rehydration at the discretion of the treating investigator. See Section [3.2.1.1.1](#) / [Table 2](#) regarding dose modifications in the setting of persistent nausea/vomiting.

#### **4.2.5 Antidiarrheal Support**

SG monotherapy in TROPHY-U-01 (IMMU-132-06), 64% of participants experienced diarrhea (all grades), with 11% experiencing Grade 3 diarrhea. Subjects who exhibit acute onset diarrhea (within 24 hours of treatment) and/or an excessive cholinergic response to treatment with SG (e.g., abdominal cramping, diarrhea, salivation, etc.) can receive subcutaneous atropine or other appropriate medication for subsequent treatments. Infectious causes of the diarrhea will be evaluated and if negative, loperamide will be administered at the onset of treatment-related Grade 1 or Grade 2 diarrhea, at an initial dose of 4 mg, followed by 2 mg with every episode of diarrhea to a maximum dose of 16 mg/day. If diarrhea is not resolved after 24 hours, consider adding diphenoxylate/atropine. Consider adding octreotide 100-150 mcg subcutaneous (SC) three times per day if diarrhea persists. IV fluids/electrolyte repletion may be administered to support rehydration at the discretion of the treating investigator.

See Section [3.2.1.1.2](#) / [Table 2](#) regarding dose modifications in the setting of persistent diarrhea potentially attributable to SG.

## 5 CORRELATIVE STUDIES FOR RESEARCH

### 5.1 BIOSPECIMEN COLLECTION

#### 5.1.1 Sample Collection Table

Test/assay	Type of tube a and volume	Collection point	Location of specimen analysis b
Blood Samples			
Circulating tumor DNA (ctDNA)	2x10mL Streck Tube	C1D1(prior to treatment), C1D8 & C3D1 (within 48 hours after the SG dose), EOT/at progression	Biospecimen Processing Core (BPC)
Circulating tumor cells (CTC)	1x10 mL Streck Tube	C1D1(prior to treatment), C1D8 & C3D1 (within 48 hours after the SG dose), EOT/at progression	DTB Clinical Translational Unit
$\gamma$ H2AX expression	2x8 mL CPT blue/black tube	C1D1(prior to treatment), C1D8 & C3D1 (within 48 hours after the SG dose), EOT/at progression	
UGT1A1 genotyping	1x6 mL Lavender-top tube (K2EDTA)	C1D1 (prior to treatment)	BPC
Tumor Samples			
TROP2 IHC	FFPE , 1 core	Archival FFPE tissue if available, C1D1 (prior to treatment, mandatory except as noted in Section 5.1.3), EOT/at progression (optional) c	BPC/LP
Evaluation of DNA damage repair and other pathway genes (Next gene sequencing, whole genome sequencing and RNAseq)	FFPE/fresh frozen tissues, 3 cores		BPC/fee-for-service Core lab
TSO500	Archival, 10 unstained slides or tissue block	Archival FFPE tissues, C1D1 (prior to treatment)	LP

- a. Please note that tubes and media may be substituted based on availability with the permission of the PI or laboratory investigator.
- b. The location of specimen analysis may be adjusted at the time the analyses are performed
- c. Biopsies may be not performed on the specific dates and times due to the following reasons, including but not limited to, delayed recovery of hematologic toxicities, delayed clinic schedule, or national holidays

